9.0 Procedures Involved*

9.1 This investigation will be divided into three parts, each associated with one of the specific aims detailed in Section 1. All procedures will be performed in the School of Allied Health Professions, either in the Motion Analysis Laboratory (Gait Lab) or the Rehabilitation Faculty Practice (RFP) Clinic.

Part 1: Compare age and gender matched healthy controls and KOA groups on kinetics, kinematics, and gait speed during self-selected speed via a between groups analysis across the dependent variables, and determine if those differences in the KOA group have a predictive relationship with their KOOS scores.

Part 2: Within-group comparison of both groups (with and without volitional TA activation) and between-groups (control group versus KOA group). Compare pain levels during both conditions via NPRS for the KOA group. Participants will wear biofeedback under both conditions, and all condition trials will be randomized. Alarm or verbal cue will be provided at 30% MVIC, and two electrodes placed over TA/obliquus internus (OI) just medial to anterior superior iliac spine (ASIS). A comparison of TA activation will be performed both within and between groups.

Part 3: Within-groups comparison of KOA group (pre-treatment and post-treatment; six-week training program) on kinetics, kinematics,

PROTOCOL TITLE: The Effects of Core Activation and Stabilization Training on Gait Kinetics, Kinematics, and Speed, and Self-Perceived Function in Patients with Knee Osteoarthritis

and gait speed during self-selected paced ambulation. A comparison of KOOS scores before and after treatment will be performed as well.

9.2 Once recruitment (see 22.0) and informed consent (see 27.0 and 28.0) are completed:

Part 1: All participants will undergo anthropometric data collection first, including weight, height, leg length, knee joint width, and ankle joint width. Age matching will be done within +/- 5 years between the two groups. Reflective markers will then be placed on bilateral lower extremities following the Plug in Gait Model. EMG electrodes will be placed bilaterally just medial to the ASIS, over the TA/OI. The Gait Lab will undergo calibration, and the participant will undergo a static trial. In participants with bilateral KOA, the most painful limb, identified by subjective report, will be used in the data collection procedures. Healthy controls will undergo analysis of their dominant limb by indicating with which leg they would kick a ball.

Once the set-up and calibration are completed, the data collection will begin. The participant will be allowed a brief warm-up of 1-2 minutes, walking in the Gait Lab prior to data collection commences. The participant will then be asked to walk at a self-selected pace across the capture area until three trials with good force plate contact are obtained. Good force plate contact is defined as initial contact at the heel and pre-swing/toe off occurring on the force plate, and the absence of any evidence of distraction via the video cameras, such as the participant talking or looking around the lab. These three trials will be used in the kinetic, kinematic, and gait speed data analysis.

See Part 2 for additional trials that will be performed concurrently for both groups. Participants in the experimental group will also be asked to complete a KOOS questionnaire at the same time.

Part 2: Participants will undergo the same procedures described in Part 1 above. While the three trials are obtained for Part 1, three additional walking trials will be concurrently collected for the both groups. These will include the participant volitionally activating their TA during the walking trials, performed and screened exactly the same as in Part 1. These trials will be performed with and without audible biofeedback (via an alarm or verbal cueing), indicating the TA meeting the threshold subsequently discussed below. Investigators will randomly determine whether the trials with or without volitional TA activation are performed first (i.e., Part 1 versus Part 2 trials). The randomization done for Part 2 to determine

PROTOCOL TITLE: The Effects of Core Activation and Stabilization Training on Gait Kinetics, Kinematics, and Speed, and Self-Perceived Function in Patients with Knee Osteoarthritis

whether or not the without (Part 1) or with (Part 2) volitional TA activation trials are performed first will be determined via random number generation between 0 and 1 in Excel. Those with 0 will perform the without volitional TA (Part 1) trials first, while those with 1 will perform the with volitional TA activation trials (Part 2) first.

The patient will lie supine on the mat in the lab and will be taught how to perform a TA contraction. Please see the attached script with the instructions that will be used in this education. A baseline maximal contraction will be performed supine, and the amplitude of contraction will be considered maximal voluntary isometric contraction (MVIC). The device will be set to provide audible feedback, or the participant will receive a verbal cue from the investigator, at 30% MVIC. This feedback will be randomized throughout the trials with TA activation via random number generation in Excel, with 0 signifying no cue and 1 indicating a cue. The task will be repeated seated, then standing, prior to data collection.

The experimental group, during both sets of trials, will be asked to subjectively rate their perceived pain in the lower extremity being used in data collection via a 10-point scale, typically used on the NPRS, although no visual will be used. Please see the supplemental script document attached to this protocol for the instructions used.

Part 3: Participants in the experimental group will participate in a six-week core stabilization intervention program. Please see the attached intervention program. This program will commence as soon as possible after Parts 1 and 2 of the investigation are completed. Participants will participate in two scheduled intervention sessions each week. Additionally, there will be a home exercise program, consisting of exercises from each week to be performed at home independently. Participants will be provided education and a handout on these exercises by the PI, which will include directions, photographs of the exercises, and a completion check-off for each session. These will be performed three times per week, every other day. The PI will be coordinator of the scheduling and performance of these interventions. These intervention sessions will be performed in the RFP Clinic in the SAHP, either in the open gym or in a private treatment room. This decision will be left up to the participant. More than one participant may or may not undergo intervention with the PI simultaneously, but only with the participants' consent. No more

PROTOCOL TITLE: The Effects of Core Activation and Stabilization Training on Gait Kinetics, Kinematics, and Speed, and Self-Perceived Function in Patients with Knee Osteoarthritis

than three participants will undergo the training simultaneously. Training sessions will not be performed on consecutive days in an effort to reduce the chances of delayed onset muscle soreness being present during treatment sessions. Additionally, the core training program includes predetermined guidelines on exercise progressions in order to ensure that the exercises are not progressed too rapidly. The PI will be present and will lead all sessions, ensuring that the exercises and their progressions are done correctly.

After the completion of the intervention program, each participant will undergo gait analysis in the same manner mentioned in Part 1, with the exception of no anthropometric data being collected.

Participants will then complete a second, post-intervention KOOS questionnaire, and turn in their home exercise program sheet with tallies from completed sessions. Please see Part 1 for completion of the pre-intervention KOOS questionnaire.

9.3 The table below details the procedures and occurrence of those procedures throughout a single participant's participation in the investigation:

Procedures	Occurrence
Education/Informed Consent	1 all participants
Anthropometric Data Collection	1 all participants
Baseline (Part 1) Without & With Core Activation (Part 2) Pre 6-Week Intervention Gait & EMG Assessment (Part 3)	1 all participants (except no part 3 for controls)
Pain NPRS Assessment	2 for KOA group
Core Stability Intervention Program	12 sessions, plus 18 home program sessions (KOA group only)
Post 6-Week Intervention Gait & EMG Assessment	1 (KOA group only)
Pre and Post 6-Week Intervention KOOS Assessment	2 (KOA group only)

9.4 The exclusion criteria serve to prevent participation of those who require assistance or assistive devices for ambulation, so safety during the ambulation activities is minimized. The adhesive tape used in reflective marker placement is intended for placement on the skin. Regarding PHI, the PI will be the only investigator involved in the recruitment and consent process and will be charged with

PROTOCOL TITLE: The Effects of Core Activation and Stabilization Training on Gait Kinetics, Kinematics, and Speed, and Self-Perceived Function in Patients with Knee Osteoarthritis

protecting the PHI in his office. The motion analysis data and PHI will be protected in the manner discussed in sections 11.3.

A tape measure, body weight scale, EMG biofeedback with electrodes, and Vicon Vero 2.2 Motion Analysis System, and reflective markers with tape will be used. Exercise equipment will include exercise mats/high-low exercise tables, ankle weights, hand weights, BOSU balls, and resistance bands.

Please see the attached Excel file that will be used for data collection, in addition to the script for instructions to patients and KOOS questionnaire.

- 9.5 There is no long-term follow-up for this study apart from the final data collection session for the experimental group after completing the six-week intervention. This session will include another motion analysis session and post-treatment KOOS questionnaire completion.
- 9.6 NA.

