1.0 Objectives*

- 1.1 The purpose of this investigation is to determine the effect, if any, core activation and stabilization training may have on the gait and function of patients diagnosed with knee osteoarthritis (KOA).

The specific aims of this investigation include:

Specific Aim 1: Determine if kinetic (time to first peak ground reaction force [T_1] and second peak ground reaction force [F_2], both in the sagittal plane, and external knee adduction moment [KAM]) and kinematic (peak stance knee flexion angle [KFA]) gait variables, and speed, differ between patients with KOA and age and gender matched controls during self-selected paced ambulation, and determine which ones have predictive relationships with Knee Injury and Osteoarthritis Outcome Score (KOOS) scores in the patients with KOA.

Specific Aim 2: Determine if volitional core activation alters gait kinetics (T_1 , F_2 , and KAM), kinematics (KFA), and speed in patients with and without KOA during self-selected paced ambulation when compared to ambulating without volitional core activation, and whether the subjective pain complaints are significantly changed in the group with KOA. Determine whether there are baseline differences in core activation between those with and without KOA.

Specific Aim 3: Determine if a six-week core stabilization program alters KOOS score, and the kinetics (T_1 , F_2 , and KAM), kinematics (KFA), and speed of gait in patients with KOA during self-selected paced ambulation as compared to their pre-intervention baselines. Determine if there is a predictive relationship between the number of completed intervention sessions performed and these observed changes.

- 1.2 The alternate hypotheses for each specific aim include the following:

Specific Aim 1:

H_1 : Participants with KOA will have significant differences in lower extremity kinetics (T_1 , F_2 , and KAM) and kinematics (KFA), and gait speed, as compared to healthy controls during self-selected paced ambulation.

H_2 : The significant kinetic (T_1 , F_2 , and KAM), kinematic (KFA), and gait speed differences observed in participants with KOA will have a significant predictive relationship to their scores on the KOOS.

PROTOCOL TITLE: The Effects of Core Activation and Stabilization Training on Gait Kinetics, Kinematics, and Speed, and Self-Perceived Function in Patients with Knee Osteoarthritis

Specific Aim 2:

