11.0 Data Management* and Confidentiality

- 11.1 Data analysis will be performed by the PI, with the assistance of the sub-investigator. The PI will use the latest version of SPSS available to the PI on his personal laptop computer (see 11.3 for security details). The kinetic, kinematic, and speed data will be analyzed together, either by a MANOVA (if assumptions are met) or separate ANOVA/mean comparison analyses with Bonferroni corrections, while the pain NPRS and KOOS scores will be analyzed each individually via means comparisons. The EMG data will be analyzed via a 2x2 ANOVA or separate means comparisons. If the groups have significantly different mean BMIs, then it will be included in the kinetic and kinematic analysis as a covariate. The predictive relationship between the number of exercise sessions and the change observed within the KOA group for each variable will be analyzed via regression analysis.
- 11.2 An *a priori* power analysis was performed to determine the number of participants required to achieve significance for the variables of highest interest in the investigation. Data from previous publications on these variables were used in the power analysis. These include the following: T₁ between¹⁶ and within ([name], [name], unpublished data, May 2018) groups, F₂ between and within groups,¹⁸ KAM between and within groups,¹⁷ KFA between¹⁴ and within²⁶ groups, and gait speed between¹⁶ and within²⁷ groups for the kinetic and kinematic analyses. Additionally, the KOOS²⁸ was examined for within-group means comparison. The PI used G*Power (Heinrich-Heine-University Düsseldorf, Düsseldorf, Germany) for the purposes of these analyses. It was determined that 45 participants would be required, except for the KFA which would require a larger sample size. Since this variable will be collected concurrently along with the other kinetic and kinematic data, and all the other variables of interest are appropriately powered at a much lower sample size, we felt confident proceeding regardless of being underpowered for one of these five dependent kinetic/kinematic variables of interest.

Since this study involves a six-week intervention, an attrition rate of 10% was assumed, so a total of 50 participants (25 healthy controls and 25 with KOA) will be recruited. Data analysis will be completed

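### Controls are matched on age and gender, but the KOA-versus-control tests adjust for neither, which costs some power and leaves any age gap inside the tolerance uncorrected

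*Combined protocol and SAP*

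**What the plan says.** Specific Aim 1 (section 1.1) asks whether gait variables "differ between patients with KOA and age and gender matched controls during self-selected paced ambulation". Section 9.1, Part 1, repeats the matching and describes the comparison only as made "via a between groups analysis across the dependent variables". Section 9.2 gives the one operational detail: "Age matching will be done within +/- 5 years between the two groups". It does not say whether each control is paired with one KOA participant or the two groups are only balanced overall.

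Section 11.1 analyses the gait variables and speed "either by a MANOVA (if assumptions are met) or separate ANOVA/mean comparison analyses with Bonferroni corrections". For EMG, "The EMG data will be analyzed via a 2x2 ANOVA or separate means comparisons". The only covariate rule is: "If the groups have significantly different mean BMIs, then it will be included in the kinetic and kinematic analysis as a covariate". No section names age, gender, a pair term or a matched-set analysis for any comparison of the two groups.

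**The concern.** Matching makes the two groups alike on age and gender, so variation from those factors largely drops out of the difference in means. An ordinary two-group test does not know this and still counts that variation as noise. Its standard error is then larger than the true sampling error, and power is lower than the same data could give.

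The tolerance raises a second question. If controls fall mostly on one side of it, the groups differ in mean age and nothing in section 11.1 corrects for that.

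The comparisons at stake are the Aim 1 contrasts on T1, F2, KAM, KFA and speed, and the Aim 2 comparisons of group level in gait and EMG. The sample is small (25 per group), section 11.2 already accepts low power for KFA, and the fallback analysis divides alpha by a Bonferroni correction.

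**Working it through.** **Plan's own figure.** Section 11.2 states "It was determined that 45 participants would be required, except for the KFA which would require a larger sample size", then assumes 10% attrition: 45 / (1 − 0.10) = 50, or 25 per group. That reproduces. The 45 itself cannot be checked, because alpha, power, effect sizes and SDs are not stated. Nothing therefore shows whether it assumed any gain from matching.

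**Inputs.** From the documents: 25 per group, matching on age (±5 years) and gender, no age or gender term. Assumed: two-sided alpha 0.05; R², the share of outcome variance explained by age and gender together, at 5, 10, 20 or 30%; age SD about 9 to 10 years.

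**Standard error, one-to-one matching.** With outcome SD 1, the planned test uses √(2/25) = 0.283. If pairs share age and gender closely, the within-pair correlation is about R², and the true SD of the difference is √(2(1 − R²)/25). The ratio is 1/√(1 − R²):
- R² = 10%: 1/√0.9 = 1.054
- R² = 20%: 1/√0.8 = 1.118
- R² = 30%: 1/√0.7 = 1.195

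The standard error is thus about 5, 12 and 20% too large.

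**Power.** An adjusted test with 50 − 4 = 46 degrees of freedom has 80% power at a noncentrality of about 2.86. The planned test's critical value (2.01 on 48 degrees of freedom) is in effect multiplied by the ratio above:
- R² = 5%: 2.86 − 2.01 × 1.026 = 0.80, power about 79%
- R² = 10%: 2.86 − 2.01 × 1.054 = 0.74, about 77%
- R² = 20%: 2.86 − 2.01 × 1.118 = 0.61, about 73%
- R² = 30%: 2.86 − 2.01 × 1.195 = 0.46, about 68%

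Simulation (8,000 trials per case, age gaps within 5 years, same gender) agrees:

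| R² | SE excess, one-to-one | SE excess, group-level | Type I error, one-to-one | Type I error, group-level | Power, planned (adjusted about 80%) |
|---|---|---|---|---|---|
| 10% | 5% | 2–3% | about 3.5% | about 4.5% | 77% |
| 20% | 12% | 3–5% | about 3% | about 4.2% | 72% |
| 30% | 20% | 6–11% | 2.0–2.3% | about 3.8% | 67% |

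The power column is for one-to-one matching; group-level matching gives a similar loss (about 76/72/66%). At alpha 0.01 (Bonferroni over five variables) the planned test has 74/69/62% against about 79%.

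The loss also depends on the effect size chosen. With the effect fixed at 0.809 SD, where an unmatched two-group test has 80% power, adjustment moves power from 81 to 82%, 82 to 85% and 84 to 93% for correlations with age of 0.2, 0.3 and 0.5 (gender effects of 0.2, 0.3 and 0.5 SD).

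**Residual age gap.** Bias in SD units = gap × correlation with age / age SD. At R² = 20% split equally between age and gender, the age correlation is √0.10 = 0.316. A 2.5-year gap with age SD 9 gives 2.5 × 0.316 / 9 = 0.088 SD. In simulation, adjustment brings the bias to about zero. At the extreme, with every control 5 years younger and age SD 10, the bias is 5 × 0.3 / 10 = 0.15 SD or 5 × 0.5 / 10 = 0.25 SD at correlations 0.3 and 0.5. Type I error of the unadjusted test is then 6.2% and 8.3%.

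**Scope.** Comparing with and without activation is within-person, so age and gender effects that are the same in both conditions cancel, and they cancel from the group-by-condition interaction too. What remains exposed is the group main effect and any single-condition group comparison. Aim 3 compares KOA participants with themselves.

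**The case against.** The strongest reply is that the planned test is not invalid. With balanced age gaps its estimate is unbiased and its false-positive rate lies below nominal, so no false claim becomes likelier. That stands.

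The excess in the standard error depends on how matching is done. The larger figures need one-to-one pairs, and section 9.2 does not say that. Under group-level matching the excess shrinks to a few percent at moderate R², and most of the remaining power gain is what any prognostic covariate would bring. This also stands, though the power loss is similar either way. The size rests on an R² that the documents do not give; if it is small, little is lost.

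A reader might infer three stronger things that the documents do not support:
- That the false-positive rate is always below nominal. A large systematic age gap can push it above, and unadjusted power is then not lower, so the two harms do not both apply in full.
- That the plan throws away power the matching was intended to provide. No section gives power as the reason for matching; comparability is an equally natural reason.
- That all Aim 2 results are affected. The within-person activation contrasts are not.

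Nor do the documents say that controls will tend to be younger or older, so the bias is a possibility and not a prediction.

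**Conclusion.** The point holds as a cheap improvement to the analysis, not as a flaw that invalidates it. The mismatch between a matched design and tests without the matching factors is plain in the text. Its size is conditional: a loss of roughly 3, 8 and 13 power points from about 80% if age and gender explain 10, 20 and 30% of outcome variance, and 1 to 2 points at 5%, with effects set so that the adjusted test has about 80% power. The standard error excess ranges from a few percent to about 20%, according to R² and the unstated form of matching. The bias from a moderate age gap is small beside the effect the sample can detect (about 0.08 to 0.09 SD against about 0.8 SD), but the plan has no means of removing it. R², age SD, alpha and power are all assumptions here.

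**What to change.** In section 11.1, state that every KOA-versus-control comparison of gait variables, speed and EMG includes age (continuous, mean-centred) and gender as covariates, whatever their observed balance. In section 9.2, say whether matching is one-to-one or at group level; if one-to-one, a pair term may be added. Covariates are preferable to a paired test alone: they also remove the residual age gap, they work under either form of matching, and they survive the loss of one member of a pair.

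The cost is one sentence in the analysis section and 2 of about 48 degrees of freedom. Both values are already needed to carry out the matching.

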3.0 Inclusion and Exclusion Criteria*

- 3.1 Potential participants will be screened for eligibility by the PI once they have expressed interest either by contacting the PI themselves, or upon being referred by someone familiar with the investigation. Assurance of meeting the inclusion and exclusion criteria will be ensured during the informed consent process.
- 3.2 The inclusion and exclusion criteria for this investigation are as follows:

Inclusion criteria:

English-speaking men and women, 40 years old and older, of any race or ethnic group, with a documented diagnosis from a medical provider (i.e., physician, physician assistant, or nurse practitioner, etc.) of KOA, unilaterally or bilaterally. Previous or current physical therapy patients may be included (see exclusion criteria for exceptions). *Healthy controls* will meet the same requirements, but without a medical diagnosis of KOA and have the ability to ambulate on a level surface without any report of pain in their knees at the time of gait assessment.

PROTOCOL TITLE: The Effects of Core Activation and Stabilization Training on Gait Kinetics, Kinematics, and Speed, and Self-Perceived Function in Patients with Knee Osteoarthritis

Exclusion criteria: those with other lower extremity injuries (orthopaedic, cardiovascular, neurologic, etc.) which are currently hindering their ability to ambulate, those with current complaints of low back pain, those who have undergone bilateral total knee arthroplasty, those with concomitant diagnosis of rheumatoid arthritis, those persons not able to ambulate independently with or without an assistive device, those who have received a corticosteroid injection within the past two months, those who have received a hyaluronic acid injection in the past six months, and those persons currently enrolled in a core training program as part of formal physical therapy or physical fitness.

3.3 Special populations will not be included in this investigation for the following reasons:

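### Limb dominance is neither matched nor adjusted for, and may partly confound the between-group comparisons of T1, F2, KAM and KFA

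*Combined protocol and SAP*

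**What the plan says.** Section 9.2, Part 1, gives two limb rules. For controls: "Healthy controls will undergo analysis of their dominant limb by indicating with which leg they would kick a ball". For one subset of cases: "In participants with bilateral KOA, the most painful limb, identified by subjective report, will be used in the data collection procedures". Section 3.2 also admits unilateral disease ("of KOA, unilaterally or bilaterally"), but no sentence says which limb is analysed then.

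Section 9.1 sets the comparison: "Compare age and gender matched healthy controls and KOA groups on kinetics, kinematics, and gait speed during self-selected speed". The only matching detail is in section 9.2: "Age matching will be done within +/- 5 years between the two groups". The only covariate rule is in section 11.1: "If the groups have significantly different mean BMIs, then it will be included in the kinetic and kinematic analysis as a covariate". The protocol text does not ask KOA participants about dominance.

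Both legs are instrumented ("Reflective markers will then be placed on bilateral lower extremities"), EMG electrodes are placed on both sides, and section 20.2 lists two force plates. Controls attend a single session (section 7.1).

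**The concern.** The rule that picks the limb depends on group. Every control contributes a dominant limb; a KOA participant contributes a limb chosen by disease or pain, which may or may not be dominant. If dominant and non-dominant limbs differ on a gait variable, part of that difference is read as an effect of KOA.

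The outcomes exposed are those that belong to one limb: T1, F2, KAM and KFA. Aim 1 H1 states: "Participants with KOA will have significant differences in lower extremity kinetics (T_1 , F_2 , and KAM) and kinematics (KFA), and gait speed". A joint MANOVA of the five gait variables would inherit the problem from these four. Aim 1 H2 then takes the variables that differed significantly and relates them to KOOS, so a shifted group contrast could change which variables go forward. In Aim 2 the exposed quantity is the group main effect.

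The direction is unknown: the offset could enlarge or hide a true group difference.

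**Working it through.** The plan states no figure on this point, so there is none to reproduce. The check traces which contrasts are exposed and then sizes the bias under stated assumptions.

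**1. Which contrasts are exposed.** Suppose dominance adds a constant offset to a limb-specific outcome.
- T1, F2, KAM, KFA between groups (Aim 1): exposed.
- The same four, group main effect in Aim 2: exposed.
- With versus without volitional activation in the same person, and the group-by-condition contrast built from those changes: the offset is in both conditions and cancels.
- Before versus after training in KOA (Aim 3): cancels, provided the same limb is analysed both times.
- Gait speed: not a property of one limb, so not exposed.
- EMG: recorded on both sides with no analysed side stated, so exposed only if one side is chosen by study limb.

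**2. Size of the bias.** Let p be the share of KOA study limbs that are dominant, and d the dominant versus non-dominant difference in SD units. Controls have share 1, so

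bias = (1 − p) × d.

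The documents give neither p nor d; all values below are assumptions.

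| p | d = 0 | d = 0.2 | d = 0.4 |
|---|---|---|---|
| 0.3 | 0 | 0.7 × 0.2 = 0.14 | 0.7 × 0.4 = 0.28 |
| 0.5 | 0 | 0.5 × 0.2 = 0.10 | 0.5 × 0.4 = 0.20 |
| 0.7 | 0 | 0.3 × 0.2 = 0.06 | 0.3 × 0.4 = 0.12 |
| 1.0 | 0 | 0 | 0 |

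**3. Scale.** Group size is 25 and 25 (sections 11.2 and 23.1). The protocol states neither alpha nor power. With two-sided alpha 0.05 and 80% power (assumed), a two-sample t test detects about 0.81 SD. At p = 0.5 the bias is then 0.10/0.81 = 12% of that for d = 0.2, and 0.20/0.81 = 25% for d = 0.4. If the Bonferroni route in section 11.1 is applied to five gait variables, alpha is 0.05/5 = 0.01, the detectable difference is about 1.00 SD, and the shares are 10% and 20%.

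**4. False-positive rate with no disease effect.** Normal approximation, standard error √(2/25) = 0.283 SD, rate = 1 − Φ(z − bias/0.283) + Φ(−z − bias/0.283).

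| Bias (p = 0.5) | alpha 0.05 | alpha 0.01 |
|---|---|---|
| 0 | 5.0% | 1.0% |
| 0.10 | 6.4% | 1.5% |
| 0.20 | 10.9% | 3.1% |

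**5. Adjusting afterwards instead of matching.** If KOA dominance were recorded but all controls stayed dominant, the correlation φ between group and dominance satisfies φ² = (1 − p)/(1 + p). The variance of the adjusted group effect rises by 1/(1 − φ²) = (1 + p)/(2p): 1.7/1.4 = 1.21 at p = 0.7, 1.5/1.0 = 1.50 at p = 0.5, and 1.3/0.6 = 2.17 at p = 0.3. At p = 0.5, φ = √(1/3) = 0.58, so confounding is partial. The dominance effect would be estimated from KOA participants alone.

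**The case against.** The strongest reply is that nothing in the documents shows a dominance effect on any of these variables. The 0.2 and 0.4 SD values have no source there, and at the lower one the false-positive rate moves only from 5.0% to 6.4%. That stands: it limits how serious the point is. It does not alter the fact that the selection rule differs by group and that neither design nor analysis deals with it.

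A reader might infer that every between-group comparison is biased. The documents do not support that. Gait speed is not limb-specific, the analysed EMG side is not stated, and a constant offset cancels in within-person and group-by-condition contrasts.

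A reader might also infer that dominance and disease cannot be separated, or that the bias could never be removed. Neither follows. KOA study limbs may be dominant or not, so the overlap is partial. If KOA dominance were recorded, a covariate or a restricted analysis would be possible at some loss of precision. Section 10.2 also keeps all force-plate and camera data, so some usable contacts from the other control limb may exist, although the plan does not require them. The obstacle is that recording KOA dominance is not planned in the protocol text; the data collection form is an attachment that was not available here.

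Two further replies stand. One-to-one pairs are never specified, so a fix must also work with group-level matching. And a painful knee might influence the answer to the kicking question, so recorded dominance in KOA may be imperfect.

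**Conclusion.** The concern holds in a limited form. Controls are always analysed on the dominant limb and bilateral KOA participants on the more painful one; dominance is neither matched nor adjusted for. It may therefore partly confound the between-group comparisons of T1, F2, KAM and KFA in Aim 1 and the group main effect for these variables in Aim 2.

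On the assumptions p = 0.5 and d from 0 to 0.4 SD, the bias is 0 to 0.20 SD, at most about a quarter of the difference detectable with 25 per group. It is zero if dominance has no effect or if all KOA study limbs happen to be dominant. This is a possible bias, not a demonstrated one. It merits a change because the remedy is cheap during the control's only session and weaker afterwards. The missing limb rule for unilateral KOA is a separate gap in the text that should be closed at the same time.

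**What to change.** - Ask KOA participants the same kicking question and record whether the study limb is dominant. Wording it in both groups as usual preference before any knee symptoms would reduce the risk that pain drives the answer.
- Write down which limb is analysed in unilateral KOA. The rule for bilateral KOA can stay as it is.
- If controls are paired to KOA participants, analyse in each control the limb with the same dominance status as the paired participant's study limb. If matching is only at group level, assign control limbs so that the share of dominant limbs is equal in the two groups. Make the choice without sight of the gait results.
- Where the match is not yet known when a control attends, collect three trials with good force-plate contact for each limb.
- If control limbs cannot be matched, add a sensitivity analysis for T1, F2, KAM and KFA comparing controls with only those KOA participants measured on the dominant limb. At p = 0.5 that leaves about 12 or 13 of the 25 KOA participants, so it would be imprecise.
- State which EMG side is analysed, and apply the same limb choice if only one side is used.

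With control limbs matched or balanced, the expected bias from a constant dominance offset is zero. The cost is one extra question and a few extra walks for controls, whose legs already carry markers on both sides.
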